2. Varenicline: Varenicline will be administered as clinically indicated and will begin approximately 4-6 weeks prior to surgery. All participants will receive a 1-week dose induction period (0.5mg QD Days 1-3, 0.5mg BID Days 4-7) before transitioning to a full maintenance dose (1mg BID). The target-quit date (TQD) will be on Day 8 (week 2) and will coincide with the 1st day of the maintenance dose, consistent with recommended guidelines. Participants will receive a 1-week supply of varenicline (with 3 days of extra doses in the event of an unpredicted event) in blister packs at each study visit. This will enable us to better track medication adherence and adverse events, and will help encourage participants to attend weekly visits. There is nothing experimental about the use of varenicline in this study. Participants will receive a 2-week supply of varenicline (with 3 days of extra doses) at the visit immediately prior to the participants’ scheduled surgery in order to allow participants to continue taking the full maintenance of varenicline uninterrupted, while also allowing for ample healing time before returning for the first study visit post-surgery.

3. Incentives: Incentive payments will begin on the TQD (week 2) and will be in place for 5 weeks or until surgery (whichever is sooner). Participants will receive monetary based incentives for biochemical evidence of smoking abstinence. Abstinence will be determined via breath carbon monoxide (CO) ratings during Week 2, and via urinary cotinine for the duration of the study. The transition from CO to cotinine is a common procedure that provides a method for awarding incentives to participants who have recently begun abstaining from smoking but will still test positive for cotinine (because of the long elimination half-life of cotinine). Cotinine-based testing will be used as the definition of abstinence during weeks 3-12. CO will be tested using mobile meters and abstinence will be

Table 2. Incentive and Compensation Structure

Study Week	Study Visit	Incentives	Visit Payments
Screening			\$30
1	-6		\$20
2	-5	\$20	\$20
3	-4	\$40	\$20
4	-3	\$60	\$20
5	-2	\$80	\$20
6	-1	\$100	\$20
7	1		\$50
8	2		\$60
9	3		\$70
10	4		\$80
11	5		\$90
12	6		\$100
Follow-up			\$50
Total:		\$300	\$650

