defined as ≤ 4 ppm. Cotinine will be tested using hand-held dipsticks and abstinence will be defined as ≤ 100 ng/ml. Incentives will be awarded immediately onsite for biochemical samples that meet the abstinence criteria during weeks 2-6. Table 2 displays the schedule of payments, which have been arranged strategically to maximize the impact of the incentives. In other words, research has shown that incentive payments that escalate over time, are high in magnitude, and include reset contingencies for positive samples are the most effective in promoting behavior change. Total possible incentive payments will be \$300. Though this value may seem high, it is important to make the incentive magnitude for this initial study high enough to determine whether it will produce the expected effect on smoking cessation and to accurately assess the study outcome measures; future studies can be conducted that vary the magnitude of the incentive to reduce overall cost of the intervention. Further, this approach will help us to determine whether the cost expenditure associated with this study will be recovered by the cost savings that we hypothesize will result from smoking cessation and the associated decrease in complications, analgesic use, and hospital readmissions, which run in thousands of dollars per complication.

In addition to the visit payments and incentives displayed in Table 2, participants will have the chance to win \$5 in bonus money at the end of each session that includes an administration of the PASAT to assess distress tolerance.

Biochemical Testing: It is important to note that results of biochemical testing will not be conveyed with the surgical team. The reason for this is that we need to ensure that patients will not falsify or attempt to misrepresent their smoking status out of concern that their results may have a negative impact on their surgery plans. All results obtained from these patients will be kept confidential from the surgical team and the surgical team will continue to assess smoking in the manner that had been used prior to the study.

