Urine will be tested for the primary outcome measure, cotinine. Cotinine testing will be conducted immediately onsite via a CLIA-waived semi-quantitative cotinine urine dipstick, NicAlert (Jant Pharmacol Corporation; Encino, CA). NicAlert provides a semi-quantitative rating of cotinine on scale of 0 (0 mg/mL) to 6 (≥ 1000 mg/mL), and abstinence is defined as having a cotinine level ≤ 2 (corresponding to ≤ 100 mg/mL). According to the package insert, NicAlert has no cross-reactivity with other nicotine-like compounds (niacinamide, nicotine, nicotinic acid, nicotinic acid n-oxide), and is not affected by numerous other commonly-used compounds (e.g., aspirin, acetaminophen, caffeine) or changes in urine conditions (e.g., pH, specific gravity, glucose, bacteria). NicAlert has been used successfully in a previous smoking cessation incentive intervention (Schepis et al., 2008). NicAlert also shows high sensitivity (88%-92.2%) and specificity (92%-97.6%) for detecting nicotine use (Bernert, Harmon, Sosnoff, & McGuffey, 2005; Marrone et al., 2011), as well as 96% agreement with GC-MS quantitative testing, and 94% agreement with semi-quantitative EMIT testing (Gaalema, Higgins, Bradstreet, Heil, & Bernstein, 2011). Urine-based NicAlert also demonstrated higher levels of sensitivity and specificity for detecting smoking compared to saliva-based NicAlert in a between-group comparison of nicotine detection methods in smokers and non-smokers (Marrone et al., 2011).

b. Study duration and number of study visits required of research participants.

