Study Visits: Participants will attend an initial in-person screening visit, described above, and will return to the clinic on approximately a weekly basis during study weeks 1-12 to receive the intensive pre- post-surgical smoking cessation intervention. Visits during the surgical week will occur prior to the surgery to allow for postsurgical recovery time and we will provide 2 weeks of medication at that visit to allow participants to continue using the medication during their recovery period and provide general flexibility to participants who are unable to complete a visit during their first postsurgical week. Each visit will include collection of a urine sample (that will be tested for urinary cotinine and illicit drug use), a breath CO sample, and self-report questionnaires. None of the data collected during study visits will be shared with the patients' surgical team. Participants will be contacted via phone approximately 3 weeks after study

completion and asked whether they are still abstaining from smoking. Those who endorse continued abstinence will be asked to complete a follow-up visit, during which they will provide a urine sample that will be tested for evidence of cotinine. Participants may be contacted over an additional six month period for follow-up questions pertaining to treatment outcome. Participants will be compensated for attending study visits and completing brief questionnaires and tasks; session payment values will escalate after surgery to encourage continued retention (a standard practice in our treatment protocols) and the total possible study visit compensation will be \$650.

- c. Blinding, including justification for blinding or not blinding the trial, if applicable.

Given that this is an open-label pilot study, all participants will receive the same intensive pre to post-surgical smoking cessation intervention in order to collect the data necessary to illustrate the feasibility of incorporating such an intensive intervention into the hospital setting. This pilot data will be used to support the need for future funding to complete larger randomized controlled trials, and/or multi-site trials. Given that no comparison condition is being included in the current pilot study, the issue of blinding is not applicable at this time.

- d. Justification of why participants will not receive routine care or will have current therapy stopped.

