There is no standard and/or routine access to smoking cessation in elective surgical patients. This study will not disrupt any ongoing routine care associated with the participant's surgery.

- e. Justification for inclusion of a placebo or non-treatment group.

N/A

- f. Definition of treatment failure or participant removal criteria.

Participants failing to continue to meet any of the inclusion/exclusion criteria will be removed from the study and an appropriate clinical referral provided. For example, subjects developing a psychiatric disorder or symptoms requiring treatment (e.g., mania, suicidality, and psychosis), major medical illnesses or serious injuries, which would preclude further participation, will be withdrawn. Subjects who consistently fail to show up for the first treatment session may also be withdrawn.

- g. Description of what happens to participants receiving therapy when study ends or if a participant's participation in the study ends prematurely.

Participants will be debriefed after completing the 1-month follow-up, 6-month follow-up, or premature removal. They will be fully informed about all treatment options for smoking cessation and provided with additional referrals as needed. Any participant who is discharged or voluntarily leaves the study will be provided referrals for obtaining assistance with smoking cessation. The participants will continue meeting with their surgical team, consistent with routine practice for post-surgical patient care and independent of the study.

6. Inclusion/Exclusion Criteria

Inclusion Criteria: We will recruit cigarette smokers who have scheduled an elective surgery to participate in the study. Inclusion criteria will include having a surgery scheduled 5-10 weeks in advance, reporting regular cigarette smoking (smoking 3 times a week or more) and providing a cotinine-positive urine sample.

Exclusion Criteria: Exclusion criteria will include being contraindicated for varenicline use, using products other than cigarettes as a primary nicotine product (including e-cigarettes), providing an illicit drug-positive urinalysis test without evidence of concurrent prescription (e.g., for narcotic pain medications, for example), being pregnant or breastfeeding, or a score >20 on the Beck Depression Inventory-II or a score ≥ 0 on the suicide question of the BDI, past year suicidal ideations or behavior on the C-SSRS, being

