- b. Justification and safety information if FDA approved drugs will be administered for non-FDA approved indications or if doses or routes of administration or participant populations are changed.

N/A

- c. Justification and safety information if non-FDA approved drugs without an IND will be administered.

N/A

8. Study Statistics

Outcome Measures: We will collect a variety of outcome measures to enable a full characterization of decision-making factors at baseline, and the impact of this intervention on smoking status, postsurgical outcomes, opioid analgesia utilization, and cost.

- a. Primary outcome variable.

Smoking Outcomes: Our primary outcome variable will be smoking status. Smoking abstinence will be defined as a negative biochemical sample + self-report of no smoking for the past 7 days, mean % negative samples, and mean continuous negative samples. Smoking will be evaluated within each pre and post-surgical phase, and collapsed over the 11-week targeted cessation period (following the TQD during week 2). Point prevalence smoking abstinence at the follow-up will be defined as a negative cotinine sample + self-report of no smoking for the past 7-days.

b. Secondary outcome variables.

Secondary smoking outcomes will include ratings of nicotine withdrawal and craving, using standardized measures, and frequency of adverse events judged to be related to varenicline or smoking cessation.

Surgical Recovery Outcomes: A variety of postsurgical outcomes will be evaluated. These will include length of hospital stay, overall quantity and frequency of opioid analgesic use, pain ratings of during the recovery period, types and frequency of post-operative complications, frequency of admission into the intensive care unit, and 30-day hospital readmission rates.

c. Statistical plan including sample size justification and interim data analysis.

Since this is an open-label study design, results will be analyzed in a mostly descriptive method.

Smoking Outcomes: Smoking outcomes will be evaluated as a function of time over the 11-week intervention. Smoking cessation rates will also be compared from the pre to post-intervention phases.

Surgical Recovery Outcomes: Surgical outcomes will be evaluated as a function of percent biochemically-confirmed smoking abstinence, to assess whether the duration and/or magnitude of smoking abstinence is statistically associated with 30-day readmission rates, opioid analgesic use, and other surgical outcomes.

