
taking the study medication at any time. Participants who request to stop taking the study medication because of potential medication-related side effects may be permitted to continue participating in the study. This will be determined on an individual basis by the study team members.

Protection Against Risks Associated with Continued Cigarette Smoking: All participants in this study will receive access to cognitive behavioral therapy for smoking cessation, which is a standard-of-care for smoking cessation and will be informed of the potential negative impact of smoking on their surgery. Despite this, some participants may not respond to the smoking cessation intervention. We will also encourage all applicants who are not eligible for this study, participants who are discontinued or participants who have completed the study to contact the Maryland Quit Line, which is a free service that provides access to NRT products as an alternative to study participation.

Protection Against Risks Associated with Pain Testing: It is likely that participants will experience some acute and transient discomfort from the pain testing session, however we will work to mitigate that risk as much as possible. First, participants will be informed of the pain testing procedure during the informed consent and will be able to make an informed decision regarding their study participation. Second, we chose pain tests (pressure pain and conditioned pain modulation) that will produce short-lived effects, and are unlikely to produce any residual pain. Third, we will stop pain administration as soon as participants report the first incidence of “pain” (operationalized as 50% on a scale of 0% (no pain) to 100% (extreme pain)). Time to first pain will serve as our dependent variable in the analyses. Fourth, we will enforce an upper limit on both pain measures to prevent any tissue damage from occurring (e.g., hand cannot be in cold pressor task for >150 seconds). Finally, participants will be informed that they can revoke their consent to participate in the pain testing at any time without penalty

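### A participant who has stopped cigarettes but uses an e-cigarette or nicotine replacement can be counted as smoking, because a negative cotinine is required from week 3

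*Combined protocol and SAP*

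**What the plan says.** - **Marker.** Section 5.a (Incentives) uses breath CO in week 2 only. After that, "Cotinine-based testing will be used as the definition of abstinence during weeks 3-12". The cut-off follows: "Cotinine will be tested using hand-held dipsticks and abstinence will be defined as ≤ 100 ng/ml".
- **Primary outcome.** Section 8.a states "Smoking abstinence will be defined as a negative biochemical sample + self-report of no smoking for the past 7 days". It also lists the percentage of negative samples and continuous negative samples, with no self-report attached to those two.
- **Follow-up.** Section 8.a: "Point prevalence smoking abstinence at the follow-up will be defined as a negative cotinine sample + self-report of no smoking", over the past 7 days.
- **What the strip detects.** Section 5.a (Biochemical Testing) cites "specificity (92%-97.6%) for detecting nicotine use". The property described is nicotine use, not cigarette use.
- **Entry.** Section 6 excludes those "using products other than cigarettes as a primary nicotine product (including e-cigarettes". Secondary use is not mentioned.
- **After completion.** Section 9.b encourages ineligible applicants, discontinued participants and completers to contact a quit line, "which is a free service that provides access to NRT products as an alternative to study participation".
- **CO data.** Section 5.b has each weekly visit include "a breath CO sample, and self-report questionnaires", but no abstinence definition uses CO after week 2. For the follow-up visit section 5.b names only a urine sample.

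**The concern.** The objectives in section 2 are about smoking, and the surgical hypotheses concern sustained smoking abstinence. From week 3 the marker measures nicotine exposure. The two differ for anyone who stops cigarettes and keeps using, or takes up, another nicotine product. No section says how to classify a participant who is cotinine-positive, reports no cigarettes and reports an e-cigarette or nicotine replacement.

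Two results are exposed. The first is the cessation rate, which is meant to show whether a signal justifies a randomised trial. The second is the surgical analysis in section 8.c, which relates recovery to the percentage of biochemically confirmed abstinence. A cigarette quitter recorded as a continuing smoker sits at the wrong end of that exposure scale.

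**Working it through.** The plan gives no figure for other nicotine use or for misclassification, so there is nothing to reproduce. The check has three parts.

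**1. Does the rule as written produce the error?** Take a participant who smokes no cigarettes and has cotinine above 100 ng/ml from another product. The self-report condition is met and the cotinine condition fails. Because both are required, the participant is not abstinent, whatever the CO reading. In the percentage-negative and continuous-negative measures the sample simply counts as positive. The strip's stated lack of cross-reactivity with nicotine does not help, since the plan itself presents the strip as detecting nicotine use.

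**2. When can each route act?**
- *Secondary e-cigarette use (section 6).* It can act throughout weeks 3 to 12, and at follow-up.
- *Nicotine replacement through the quit line (section 9.b).* It can act at follow-up only. Sections 5.a and 5.b place follow-up about a month after study completion, with a telephone call at about 3 weeks that asks about smoking. Someone who has stopped cigarettes and uses nicotine replacement would truthfully report abstinence, be invited in, and could then test positive. Section 5.g, however, puts debriefing and referral after the follow-up, so the order of events is unsettled.

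**3. How large could it be?**
- Point prevalence: 1/20 = 5 percentage points per person; 2/20 = 10.
- Percentage of negative samples: weeks 2 to 12 give 11 weekly samples, 1 by CO and 10 by cotinine. A person off cigarettes throughout but positive at every cotinine visit scores at most 1/11 = 9% instead of 100%. Before surgery (weeks 2 to 6) the score is at most 1/5 = 20% instead of 100%. This assumes the week 2 CO sample counts and all visits are attended.
- Illustration for the group: let q be the true cigarette-quit rate and u the share of quitters using other nicotine. Assume every such user tests positive and everyone else is classified correctly. Expected number misclassified = 20 × q × u; observed rate = q(1 − u); chance of at least one = 1 − (1 − qu)^20. The value q = 60% is the upper short-term rate cited in section 4, not a design assumption; q = 30% and all values of u are my assumptions.

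| q | u | Misclassified of 20 | Observed rate | Chance of at least one |
|---|---|---|---|---|
| 30% | 5% | 0.3 | 28.5% | 26% |
| 30% | 10% | 0.6 | 27% | 46% |
| 30% | 30% | 1.8 | 21% | 85% |
| 60% | 5% | 0.6 | 57% | 46% |
| 60% | 10% | 1.2 | 54% | 71% |
| 60% | 30% | 3.6 | 42% | 98% |

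At q = 60% the loss runs from 3 to 18 points. For scale, the exact 95% interval for 12/20 is 36% to 81%.

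**The case against.** Several points on the other side have force.

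- **The outcome does not rest on cotinine alone.** Section 8.a pairs it with self-report in the point-prevalence definitions. That is correct, but the pairing cannot rescue a cotinine-positive quitter.
- **Participants are not told to use nicotine replacement.** A reader might infer from section 9.b that the study directs them to it. The text only encourages contact with a service that offers it, and contact need not lead to use.
- **Dual use is not expressly permitted.** That it is possible is inferred from the word primary in section 6.
- **Incentives work against it.** In weeks 3 to 6 a cotinine-positive sample forfeits payment: $40 + $60 + $80 + $100 = $280 of the $300 available. This is a real deterrent before surgery. Incentives stop by surgery, while the cotinine definition continues to week 12 and follow-up.
- **Section 5.f removes those who cease to meet the criteria.** A quitter whose e-cigarette becomes the primary product might be withdrawn. That would lose a cigarette quitter from the data. Read literally, the rule would also remove every successful quitter, so it cannot settle the matter.
- **Occasional use may stay at or below 100 ng/ml.** The documents do not show otherwise.
- **A strict nicotine endpoint is defensible** in a single-arm, mostly descriptive pilot, and its error is conservative. This is a good reason to keep cotinine as the main definition. It does not supply the missing classification rule, and the plan describes its endpoint as smoking.

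**Conclusion.** The gap is real: the rule as written can score a cigarette quitter as smoking, and no section provides for that case. Taken alone, this pulls estimated cigarette cessation downward. Its size is unknown. The firm figure is 5 percentage points of point prevalence per affected person among 20; the table shows what assumed frequencies would imply and estimates nothing.

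Two stronger readings are not supported. One is that non-smokers will be miscounted: the documents give no frequency of other nicotine use, and a participant must exceed the cut-off to be affected. The other is that quit-line nicotine replacement taken up after completion distorts the surgical analysis. Only concurrent use during treatment can misclassify that exposure; later uptake reaches the follow-up result alone, and only if contact comes before the visit.

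This is an analysis rule that should be added. It does not undermine the design.

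**What to change.** Keep negative cotinine plus 7-day self-report as the main definition. Then:

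1. In section 8.a, prespecify a parallel cigarette-abstinence classification. At any visit where the participant reports e-cigarette or nicotine-replacement use, classify by CO ≤ 4 ppm (the plan's own cut) plus 7-day self-report of no cigarettes. At all other visits use the main definition. Report both results, and run the surgical analysis with both exposure versions.
2. Make e-cigarette and nicotine-replacement use explicit items in the weekly timeline follow-back, which already covers tobacco and other drugs or medications.
3. At follow-up, record non-cigarette nicotine use and take a CO reading. The follow-back is specified for baseline and weekly use only, so without this step the rule has no trigger at that visit.
4. State when completers are told about the quit line relative to the follow-up visit, so that sections 5.g and 9.b agree.

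The cost is a short addition to section 8.a, a few questionnaire items, and one extra CO reading with meters already in use. Incentive rules need not change. The downside is that CO detects only recent smoking. Someone who smoked earlier in the week and reports only other nicotine could pass, so the CO-based result may be somewhat favourable and should be read beside the cotinine result.
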